17.2 ULTRASOUND SECURE TRANSFER PROTOCOL

Under the strict supervision of Indiana University data stewards, we will utilize IU BOX HEALTH, an online cloud storage and collaborative environment. IU BOX HEALTH accounts can only be set up via application to the IU data stewards for storage of critical health data. Access to these secure storage sites are then shared with vetted users. Two dedicated BOX HEALTH accounts will be set up for BLUSHED AHF.

All sites currently use Q Path, a vendor based Ultrasound storage system. All sites plus the Core Lab use Q Path in their day to day storage and review of US images. Images are securely transferred via wireless transmission from US machines to Q Path with PHI. All images are stored securely under HIPAA grade security systems. From Q Path, images are then exported to individual computers. During this transfer, PHI is NOT transferred. The only identifying cues left are date/time stamp, which may also be removed. Additional, non-identifiable labels will be added for study purposes. These will then be uploaded into BOX HEALTH.

Two BOX HEALTH folders will be created, one for the investigators and the other for the Core Lab. Prior to uploading to the Core Lab, the images will be de-identified to site by the database manager. Furthermore, the images will be scrambled to avoid interpretation by acquisition order. This further minimizes bias by forbidding site knowledge and order of acquisition. The de-identified images (both by site and PHI) will then be uploaded to the Core Lab BOX HEALTH storage folder for review by the Core Lab.

All interpretations by the Core Lab will be entered into REDCap.

17.3 CORE LAB PROCEDURE AND LUNG ULTRASOUND PROTOCOL

Introduction

The correlation between B-lines on lung ultrasound and AHF has been well-established. B-lines are an assessment of extra vascular lung water (EVLW). Past studies demonstrate correlation of B-line artifacts with the following: (1) natriuretic peptide levels, (2) invasive hemodynamics, (3) chest xray, (4) clinical assessments, and (5) computed tomography.¹⁻⁵ Moreover, B-lines may resolve after treatment.⁶ Lung ultrasound has an additional advantage: it measures patient's clinical status in real time. Finally, lung ultrasound is easily reproducible and does not carry any radiation exposure risk; thus, it can be repeated at regular intervals without increased risk to the patient.

Lung Ultrasound (LUS) Protocol

To best determine the potential value of EVLW measurements using LUS, we will assess patients at multiple timepoints throughout hospitalization.

For diagnostic purposes, previously published protocols have been the most well-studied.

Each LUS scan consists of 8 sectors as seen in figure 2. (Figure reproduced from Volpicelli et.al.⁷) Trained research personnel will record and count B-lines in each sector as visualized through one respiratory cycle at each of the time points listed in the Figure. At minimum, each stored video clip will be 6 seconds in length. The total number of B-lines for all 8 sectors will comprise the overall score. With training, the entire scan takes less than 10 minutes.

As patient positioning may impact B-lines, patients will be placed at approximately 45 degrees for all scanning. The CRF will be marked if patients are unable to lie at this angle.

- An 8 zone LUS scan will be done at the following times:
 - T00: initial LUS scan (in ED for screening and eligibility)
 - T02: 2-4 hours after initial treatment (in ED) (+/- 30 minutes)
 - T06: 2-4 hours after T02 or pre-ED discharge, whichever comes first (+/- 60 minutes)
 - T48: up to 48 hours after initial scan (Day 3) (+/- 12 hours)

Data Collection Form

- B lines

- Pleural effusion size and location
- Who is performing the scan
- Document time to perform scan
 - Begin with time stamp of first image and end with time stamp of last image +6s

Training

- Fill out pre-survey
- Watch training video on LUS and scanning protocol (15-20 minutes)
- Review 23 clips together with US director (20 minutes)
- Hands-on scanning (30 minutes)
- Perform 25 clips that have been reviewed by US director and signed off on prior to enrolling a patient (>75% of clips have B lines)
- 20% clips are reviewed by LUS Core Lab ([name])
- Correlation coefficient

Materials

Each site will have an ultrasound machine capable of performing video image recording as well as a low frequency curvilinear or abdominal (2-5MHz) probe. B-lines are US artifacts and machine software may attempt to 'clean up' images, thereby minimizing the appearance of B-lines. Therefore, machine settings at each site will be optimized for B-line visualization. To ensure consistency, the same machine with the same settings will be used for serial exams.

To the extent possible, it is preferable that sites use the same machine to facilitate standardization. For example, if the emergency department has a Sonosite Micromaxx or later model, we can standardize the protocol so that the depth is set at 18 cm, the probe is the 2-MHz abdominal probe and the setting is the abdominal preset. For sites that do not have the same equipment, a standard scanning protocol will be established for each specific machine, with the following requirements:

- 1) A low frequency curvilinear probe will be used for all image acquisition (2-5MHz)
- 2) The depth will be set to 18cm
- 3) The gain settings will be standardized for all scans at each specific site. If equipment is the same, the gain will be standardized.

[figure not shown]
Training

All physicians and research staff will undergo in-person training sessions led by the US PI at each site using a standard protocol. Both didactics and proctored bedside scans will occur. This will ensure technique and equipment settings are standardized. Published literature provides strong evidence that LUS can be learned with minimal training: as little as 30 minutes yields excellent correlation with expert sonographers.^{40,48} In addition, established protocols will be utilized for transfer and storage of images.

To ensure ongoing quality assurance, feedback will be provided to each site for every 10 patients, or more frequently as needed if initial review suggests inconsistency. An independent, blinded, expert ultrasonographer will review the images. Concordance with clinical site interpretations will be provided. Additional training will be provided by the

central reviewer as needed. Inter-rater agreement on B-line counts will be reported at the end of the study.

Figure 3: Counting of B-lines using Lung Ultrasound

lines. Half the rib space will be 5. 10 will be the maximum number of B lines per sector.

Image Review

All images will be saved as 6-second video clips. Investigators or study staff will label each clip at the time of scan post-enrollment. For example, Scan 0 is at time of enrollment. Scan 24 is 24 hours post-enrollment, Scan 72 is 72 hours post enrollment. All images will also be date/time stamped, which will be recorded in the local site CRF. Investigators or study staff will fill out a table of their count of B-lines, which will be compared to the Core Lab review. If a rib space is completely whited out with B-lines, this will count as 10 B-lines, half the rib space will count as 5. Importantly, the Core Lab will be blinded to the investigator B-line count.

No PHI will be recorded, only a study ID. Each site will separately and securely store linkages from PHI to the study ID per local IRB approved protocols. Currently, all sites have internal processes to store images for quality control as part of their training programs for fellows and residents. Images will then be transferred to a secure, password protected, access limited server with HIPAA grade security.

Local sites will review images to ensure deidentification. Once de-identified, images will be uploaded to a secure, local server with HIPAA grade security. No post-processing will occur. However, prior to upload to the Core Lab, images will be deliberately mixed with other study patients. This is being done to avoid readers from having 'before and after' images. Images will be then uploaded in batches of 5 patients to a secure, HIPAA grade server.

The Core Lab will then download the images. Importantly, the Core Lab will NOT be a study site to minimize any potential bias or failures of de-identification. Furthermore, the Core Lab will not have access to any clinical information on the patient, further limiting the potential for clinical information to bias image interpretation. To minimize the potential bias of having a single sites images reviewed, images from one site will be mixed with other sites upon arrival at the Core Lab. Reviewers will not see images of patients in chronological order or from only one site at a time.

Formal interpretations will be recorded on a standardized, secure CRF accessible only to the Core Lab and the Data Coordinating Center at IU. All investigators will NOT have access to this data until database lock. Applicable back up and secondary storage will occur on a daily basis

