4 STUDY DESIGN AND ENDPOINTS

4.1 DESCRIPTION OF THE STUDY DESIGN

A two-site, prospective, randomized, pilot trial comparing a nitrate intense vs. diuretic intense strategy. All potential ED patients will receive an initial LUS scan. Performing LUS is within the standard of care and will be done at no cost to patients. It is not frequently used however, either for diagnosis, prognosis, or to guide clinical therapy. However, treating clinicians will be blinded to these results. If clinicians choose to perform their own LUS, those patients will not be excluded. Patients who provide written informed consent and meet all inclusion and no exclusion criteria will be randomized 1:1 to either study arm. For randomized patients, study protocol will continue until there is a decrease in B-

lines to ≤ 15 or 6 hours of care has been delivered. Subjects who are hospitalized prior to the completion of the 6 hour protocol may continue on the protocol until the six hour treatment window is concluded. All images will be stored and overread by an independent, expert ultrasonographer blinded to treatment arm.

Safety of patients are paramount. If a potential life threatening etiology is identified, the clinical team will be made aware immediately, irrespective of randomization arm. These occurrences will be recorded in the eCRF. While this will be a rare event, we will a priori establish that an additional patient will be accrued into the study and an additional modified intent to treat population for analysis will be performed, excluding these patients where a life-threatening etiology was identified (i.e. pericardial tamponade).

For patients who do NOT meet eligibility criteria, the results of their LUS will be provided to the clinical team as requested.

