4.2.1 PRIMARY ENDPOINT

The total number of B-lines at the conclusion of ED AHF management

Main Secondary Endpoints:

Dyspnea will also be assessed using a 5-point and 7-point Likert scale.

B-lines ≤ 15 at the conclusion of ED AHF management

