10.4.3 ANALYSIS OF THE PRIMARY EFFICACY ENDPOINT(S)

The total number of B-lines at the conclusion of ED AHF management

We will examine the distribution of B-lines measurements for the groups with and without events separately. Both absolute number and relative change will be evaluated. Receiver Operating Characteristic (ROC) curves will be plotted together with area under the curve (AUC) calculated to understand the prediction performance of the B-line measurements. Sensitivity, specificity, positive and negative predictive values will be computed at a number of thresholds of B-line measurements to understand the trade-off between false positive and false negative. Confidence intervals of statistical measures will be constructed using the bootstrap method.⁹¹ Although 15 B-lines have been previously identified as a valid threshold, an alternative number may be more useful in the ED setting.

Potential covariates will also be considered in a logistic regression setting to improve precision, which includes baseline co-morbidities, baseline medications (in particular guideline recommended therapies) in-hospital medications, baseline renal function, serum sodium, natriuretic peptide levels, troponin levels, renal function, baseline blood pressure, and discharge medications. Variables such as physical exam, other vital signs, and hemoconcentration may also be included. These covariates are known markers of risk and are standard of care assessments for the vast majority of AHF admissions. Covariates with univariately significant association with the outcome will be included together with the treatment indicator in a logistic regression model. Due to limited sample size, we will limit the number of covariates (including treatment indicator) such that there is 10 events per covariate.

ANALYSIS OF THE SECONDARY ENDPOINTS

1. Dyspnea will also be assessed using a 5-point and 7-point Likert scale.

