10.6 MEASURES TO MINIMIZE BIAS

10.6.1 ENROLLMENT/ RANDOMIZATION/ MASKING PROCEDURES

Each site will be provided a block randomization table with variable block sizes of 2, 4, and 6. The data coordinating center will continuously monitor the recruitment until the targeted sample size is reached. We will utilize the REDCap Randomization module for web-based randomization.

Due the nature of the intervention and the clinical setting, this is an unblinded trial.

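### The plan does not say whose B-line count is the primary endpoint, and its only scoring text points to unblinded site staff although a blinded read of all images is planned

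*Combined protocol and SAP*

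**What the plan says.** Section 4.2.1 gives the primary endpoint as "The total number of B-lines at the conclusion of ED AHF management". Section 10.4.3 repeats it and adds "Both absolute number and relative change will be evaluated". Neither names a reader.

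The text that says how the score is formed is in 17.3, within the training materials: "Trained research personnel will record and count B-lines in each sector as visualized through one respiratory cycle", and, after a sentence on clip length, "The total number of B-lines for all 8 sectors will comprise the overall score".

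On blinding, 10.6.1 says "this is an unblinded trial". Section 4.1 keeps the ultrasound result from treating clinicians, but no section keeps the arm from the staff who scan and count.

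A blinded read is planned as well. Section 4.1 says "All images will be stored and overread by an independent, expert ultrasonographer blinded to treatment arm". Under 17.2 and 17.3 the Core Lab is not a study site, has no clinical information, does not see the site count, and receives images mixed across patients and sites. The uses that 17.3 states for the central review are comparison with the site count, feedback to sites, concordance and inter-rater agreement. The end of 17.3 also calls the Core Lab reads formal interpretations, kept on a restricted CRF and withheld from investigators until database lock.

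**The concern.** Every scan is due to have two counts, one by site staff who may know the arm and one by a blinded reader, and the plan does not say which is analysed. A statistician who looks for a definition of the score will find the site count first.

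B-line counting involves judgement: 17.1 asks the operator to estimate how much of the footprint is whited out and to adjust the count from there. The baseline scan precedes randomisation, but the endpoint scan does not. Knowledge of the arm could therefore shift the final count, and with it both the absolute and the relative-change comparison. The secondary endpoint of 15 B-lines or fewer (4.2.1) and the exploratory time to reach it (4.2.2) are also exposed, since one line either way decides a patient near the cut-off.

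There is a second risk. If the choice stays open until both sets of counts can be seen, it can be made with the results in view.

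**Working it through.** **Inputs.** Section 10.5 gives a target difference of 7 B-lines, an effect size of 0.7, 35 patients per arm, two-sided alpha 0.05 and 82% power. The size of any counting bias is not in the documents; every lean below is an assumption.

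**Step 1: implied SD.** 7 / 0.7 = 10 B-lines.

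**Step 2: reproduce the plan's power.** For a two-sample t-test, df = 2 × 35 − 2 = 68 and the noncentrality is λ = (difference / SD) × √(35/2). For a difference of 7, λ = 0.7 × √17.5 = 2.93. The noncentral t gives 82.3%, and the normal approximation 83.4%. The stated 82% is correct, so there is no sample-size error here.

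**Step 3: add a counting lean when there is no true difference.** Let b be the between-arm shift due to counting alone. Then λ = (b / 10) × √17.5, and the rejection rate is the two-sided noncentral t probability on 68 df.

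| Assumed lean b (B-lines) | b as share of 7 | λ | Trials with p<0.05 |
|---|---|---|---|
| 0 | 0% | 0 | 5% |
| 1 | 14% | 0.42 | 7.0% |
| 2 | 29% | 0.84 | 13.1% |
| 3 | 43% | 1.25 | 23.6% |
| 3.5 | 50% | 1.46 | 30.3% |
| 5 | 71% | 2.09 | 54.1% |

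**Step 4: the same lean when the true difference is 7.** A lean of 3 that favours nitrate makes the apparent difference 7 + 3 = 10 and raises power to 98.5%. A lean of 3 against nitrate makes it 7 − 3 = 4 and lowers power to 37.8%. The bias can therefore hide a real effect as well as create a false one.

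**Step 5: dependence on scale.** Only b / SD enters the formula. With an SD of 20, leans of 4, 7 and 10 would be needed for the same 13%, 30% and 54%. The scale itself is unsettled. Section 17.1 caps a sector at 20, so eight sectors give at most 8 × 20 = 160. Section 17.3 (image review) caps it at 10, so the most is 8 × 10 = 80. The SD of 10 and the threshold of 15 both depend on which cap applies.

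**Step 6: effect of naming the Core Lab count.** N stays at 70 and power at 82.3%, provided that the SD of 10 and the 7-line difference also apply to that read. The documents give no SD by reader.

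**The case against.** A reader might infer that the plan defines the primary endpoint as the site count. The documents do not go that far. Sections 4.2.1 and 10.4.3 name no reader. In 17.3 the summation rule is a separate sentence that also names none, and it stands in training material. Nor is the Core Lab read described only as a quality check: calling it a formal interpretation and withholding it until lock fits endpoint data equally well. This objection stands, and it limits the point to a reader left unspecified, with the nearest text pointing the wrong way. It does not settle the matter in favour of the Core Lab. The surrounding text names a different study (17.2) and labels scans at 24 and 72 hours (17.3) that do not match this trial's schedule, so intent cannot safely be read from it.

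Two further inferences are tempting but unsupported:

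- The line "20% clips are reviewed by LUS Core Lab" might seem to contradict the overread of all images in 4.1. It stands in a training list, directly after the clips to be signed off before a first enrolment, and most likely concerns certification. It needs a label and is not evidence of a partial overread.
- The remark "The only identifying cues left are date/time stamp, which may also be removed" might seem to undo the blinding. A time stamp could show scan order but not arm, and the scan schedule is the same in both arms.

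It is also fair to say that this is a small exploratory pilot, that the leans in the table come from no section of the plan, and that the 54% figure needs a lean equal to 71% of the target difference. The percentages therefore show sensitivity; they do not predict what will happen.

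**Conclusion.** The concern holds as an unspecified measurement with an avoidable bias attached. The plan does not say which count is the primary endpoint; its only scoring text points to staff who are not blinded to arm; and the blinded alternative is already planned for all images. The harm arises if the site count is analysed, which the present text permits.

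Its size is conditional. With SD 10, 35 per arm, a t-test and no true difference, an assumed lean of 2 B-lines takes the false-positive rate from 5% to about 13%, a lean of 3.5 to about 30% and a lean of 5 to about 54%. No document figure shows which lean, if any, would occur.

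A Core Lab read would remove bias in counting but not in image acquisition. Under 17.1 the operator searches each zone for the area with the most B-lines, and the Core Lab sees only the clips that were kept.

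**What to change.** 1. State in 4.2.1 and 10.4.3 that the primary endpoint, and the secondary endpoint of 15 B-lines or fewer, use the blinded Core Lab count for both the baseline and the endpoint scan. Using one reader for both keeps the relative change coherent.
2. State that the site count serves eligibility and bedside use, where it is the only count available in time, and is analysed as a sensitivity analysis.
3. Reconcile the per-sector maximum in 17.1 (20) with that in 17.3 (10), so that both reads use one scale. Check that the SD in 10.5 and the threshold of 15 refer to that scale.
4. Say in the plan that acquisition bias remains, and that a Core Lab result of 15 or fewer may disagree with the bedside count used for eligibility and for the protocol end point in 4.1.
5. Label the 20% line in 17.3 as training-only if that is what it means.

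The cost is mostly wording, because the full overread is already planned, and N does not change. Settling the scale takes a decision, and the primary endpoint becomes available only after the Core Lab has finished reading. The text should be fixed before anyone can compare the two sets of counts by arm.
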